1.3 Risk/Benefit

The ADX-629-COVID-19-001 clinical trial will evaluate the safety, tolerability, efficacy, and PD of ADX-629 in COVID-19-positive subjects with moderate severity prior to the requirement for mechanical ventilation. Scientific data suggest that a benefit to the subjects may exist from participating in the clinical trial.

The protocol design, dose selection, and safety monitoring are developed following the Food and Drug Administration (FDA) Guidance for Industry for Estimating Maximum Safe Starting Dose in Initial Clinical Trials, 2005; the FDA Guidance for Industry for Toxicity Grading Scale for Healthy Adult and Adolescent Volunteers Enrolled in Preventive Vaccine Clinical Trials, 2007; the European Medicines Agency (EMA) guidance on first-in-human and early clinical trials (EMA, 2017); and the Common Terminology Criteria for Adverse Events (CTCAE) version 5.0.

Safety of the clinical dosing regimen in this clinical trial is supported by a Phase 1 clinical trial in healthy volunteers and a number of preclinical toxicology and PK studies during which no serious safety concerns were noted at the projected therapeutic doses in humans.

Refer to the Investigator's Brochure for additional information.

2 CLINICAL TRIAL OBJECTIVES

2.1 Primary Objective

The primary objective of this clinical trial is to evaluate the safety and tolerability of ADX-629, administered orally, in adult subjects with COVID-19 of moderate severity prior to the requirement for mechanical ventilation.

2.2 Secondary Objectives

The secondary objectives of this clinical trial are the following:

- To evaluate the National Institute of Allergy and Infectious Diseases (NIAID) 8-point ordinal scale for COVID-19 scores of adult subjects with COVID-19 of moderate severity who were administered ADX-629 orally; and
- To assess the PD by measuring plasma RASP in adult subjects with COVID-19 of moderate severity who were administered ADX-629 orally.

3 CLINICAL TRIAL DESCRIPTION

3.1 Summary of Clinical Trial Design

ADX-629-COVID-19-001 is a Phase 2a, randomized, double-blind, placebo-controlled, clinical trial to evaluate the safety, tolerability, efficacy, and PD of ADX-629, administered orally, in adult subjects with COVID-19 of moderate severity prior to the requirement for mechanical ventilation. Approximately 30 subjects will be randomized in a 2:1 ratio (ADX-629 to placebo) to receive either ADX-629 300 mg BID or placebo BID for up to 28 days.

The reason for hospital admission (for hospitalized subjects), the standard of care (see Section 5.6.3) followed for each subject and site, and whether any care decisions were based on resource limitations will be clearly documented for all subjects.

Treatment will begin on Day 1 following randomization. In addition to ADX-629 or placebo, all subjects will receive standard of care treatment for COVID-19. Treatment may commence whether a subject is hospitalized or is treated as an outpatient at Screening. During the Treatment Period (Days 1 to 28/End of Treatment [EOT]), all subjects will receive study drug (either ADX-629 or placebo) BID. The study drug will continue to be taken on an outpatient basis if a subject is discharged from the hospital prior to Day 28 for hospitalized subjects. If a subject is placed on mechanical ventilation and/or is otherwise unable to ingest an oral tablet, dosing will be stopped. However, the subject will continue to be monitored for efficacy and safety. Dosing of the study drug may resume once the subject is able to safely ingest an oral tablet.

All subjects will also have an assessment using the NIAID ordinal scale score (see Appendix C) daily on Days 1 to 28/EOT. The NIAID score will be evaluated directly for inpatient subjects and assessed via a subject diary for outpatient subjects through Day 28.

After treatment is completed, subjects will undergo a follow-up visit on Day 35 (± 3 days) and a telephone follow-up on Day 60 (± 3 days). The purpose of the telephone follow-up is to assess survival status and evaluate for COVID-19 relapse. A telephone follow-up visit may be performed in lieu of the Day 35 follow-up visit if the subject is unable to attend in person.

The clinical trial will be conducted at approximately 3 sites in the United States.

3.2 Data and Safety Monitoring Board

An independent Data and Safety Monitoring Board (DSMB) with multidisciplinary representation will be established to evaluate accumulating clinical trial data and to assess the ongoing safety of the clinical trial for the subjects enrolled. Interim safety assessments will be scheduled after the first group of 10 subjects has been enrolled and subsequently, as needed, to provide safety oversight for subjects in the clinical trial. Additional details will be provided in the DSMB charter.

3.3 Stopping Criteria

An independent DSMB will evaluate the safety and tolerability of the first 10 subjects after dosing and determine if it is acceptable to continue the clinical trial. However, safety and tolerability data will be reviewed on an ongoing basis by the Medical Monitor and stopping rules will be applicable starting with dosing of the first subject.

3.4 Clinical Trial Indication

The indication for this clinical trial is the treatment of inflammation associated with COVID-19.

4 SELECTION AND WITHDRAWAL OF SUBJECTS

4.1 Inclusion Criteria

Subjects meeting all of the following criteria will be considered eligible for the clinical trial:

1. Is a male or female ≥ 18 years of age at Screening;
2. Is willing and able to sign and date (or has a legally authorized representative willing to sign and date) a written (or electronic) informed consent form (ICF) or provide equivalent consent per FDA guidelines on COVID-19 clinical trials;
3. Has a documented, laboratory-confirmed SARS-CoV-2 infection as determined by polymerase chain reaction (PCR), a SARS-CoV-2 antigen test, or another commercial or public health assay, within 3 days (72 hours) of randomization;
4. Has COVID-19 of moderate severity, as defined by the following:
 - Positive testing by standard reverse transcription PCR assay or equivalent testing;
 - Symptoms of moderate illness with COVID-19, which could include any symptom of mild illness or shortness of breath with exertion;
 - Clinical signs suggestive of moderate illness with COVID-19, such as respiratory rate ≥ 20 breaths per minute, saturation of oxygen $>93\%$ on room air at sea level, or heart rate ≥ 90 beats per minute; and
 - No clinical signs indicative of severe or critical severity (see Appendix E);

5. [REDACTED]

6. Is willing to use an effective form of contraception (all women of childbearing potential [WCBP] or men with a female partner of childbearing potential) during the clinical trial and for 90 days after the last dose of study drug.

Note: A WCBP is defined as any female, regardless of sexual orientation, who has not undergone a hysterectomy, bilateral oophorectomy, or bilateral tubal ligation or has not been naturally postmenopausal for at least 12 consecutive months (i.e., has had menses at any time in the preceding 12 consecutive months) with a negative follicle-stimulating hormone (FSH) test. An FSH test will be performed at Screening in all naturally postmenopausal women to confirm menopausal status.

Note: Sperm donation is also prohibited during the clinical trial and for 3 months after the last dose of study drug.

4.2 Exclusion Criteria

Subjects meeting any of the following criteria will be excluded from the clinical trial:

1. Has an NIAID ordinal scale score <5 (see Appendix C);
2. Is on high-flow oxygen or any form of noninvasive ventilation, excluding continuous positive airway pressure (CPAP) alone for sleep disorders (e.g., obstructive sleep apnea);
3. [REDACTED]
4. [REDACTED]
5. Has a history of chronic obstructive pulmonary disease or bronchial asthma requiring continuous treatment and/or intermittent or continuous oxygen within the last 90 days prior to Screening or has significant lung infiltrates on chest X-ray (e.g., involving >50% of lung fields) at Screening as determined by the Investigator;
Note: Intermittent use of a β 2-agonist inhaler is allowed.
6. Has had any form of mechanical ventilation (invasive or noninvasive, excluding CPAP alone) for structural lung disease, neuromuscular disease, or another condition requiring chronic mechanical ventilation;
7. [REDACTED]
8. [REDACTED]
9. [REDACTED]
10. Has a history of human immunodeficiency virus (HIV), hepatitis B, or hepatitis C infection or has a positive HIV antibody, hepatitis B surface antigen (HBsAg), or hepatitis C virus (HCV) antibody result at Screening;
11. Has a current or previous severe allergy and/or hypersensitivity to ADX-629 or its excipients;
12. Is pregnant or lactating or plans to become pregnant during the clinical trial;
Note: A serum human chorionic gonadotropin (hCG) test will be performed in all WCBP at Screening.
13. Is male and has known hypogonadism and hypospermia;

14. Is currently on another systemic immunomodulatory therapy (e.g., corticosteroid, calcineurin inhibitor, hydroxychloroquine, anti-cytokine therapy, Janus kinase inhibitor) except for daily prednisone (or corticosteroid equivalent) ≤ 10 mg/day or inhaled or nasal corticosteroids;

Note: Dexamethasone 6 mg daily or equivalent is permitted after randomization at the Investigator's discretion for progression to severe or critical COVID-19 requiring invasive ventilation or oxygen therapy for hypoxemia.

15. Is currently taking duloxetine, bupropion, a statin, a phosphodiesterase inhibitor, midazolam, fluoxetine, fluvoxamine, fluconazole, or ciprofloxacin; is on another cytochrome P450 (CYP)1A2, 2B6, or 3A4 sensitive substrate; or is on a CYP1A2, 2C19, or 3A4 inhibitor that, in the opinion of the Investigator in consultation with the Medical Monitor, would result in either supratherapeutic or subtherapeutic drug levels, placing the subject at undue risk by participating in the clinical trial;

Note: ADX-629 may increase the metabolism of other sensitive CYP1A2, 2B6, or 3A4 substrates (see Appendix D), potentially leading to subtherapeutic drug levels. Subjects taking these medications may be included; however, enrollment will be decided upon on an individual basis by the Investigator in consultation with the Medical Monitor.

16. Is currently taking any investigational products, other than the study drug;

17. Has participated in any other interventional clinical trial within the past 90 days or within 5 half-lives of the investigational therapy at Screening; or

18. Has any other condition that, in the opinion of the Investigator, could interfere with (or for which the treatment might interfere with) the conduct of the clinical trial or interpretation of the clinical trial results or that would place the subject at undue risk by participating in the clinical trial.

4.3 Withdrawal Criteria

Participation of a subject in this clinical trial may be discontinued for any of the following reasons:

- Withdrawal of consent or a subject request for discontinuation from the clinical trial for any reason;
- Occurrence of any medical condition or circumstance that exposes the subject to substantial risk and/or does not allow the subject to adhere to the requirements of the protocol;
- Any SAE, clinically significant AE, severe laboratory abnormality, intercurrent illness, or other medical condition which indicates to the Investigator that continued participation is not in the best interest of the subject;
- Pregnancy;
- Requirement of prohibited concomitant medication;
- Subject failure to comply with protocol requirements or clinical trial-related procedures; or
- Termination of the clinical trial by the Sponsor or the regulatory authority.

Unless a subject withdraws consent for further follow-up, subjects who discontinue study drug (ADX-629 or placebo) will continue with the clinical trial for acquisition of safety and efficacy assessments through the Day 60 telephone follow-up visit. If a subject withdraws prematurely from

the clinical trial prior to the EOT visit (Day 28), clinical trial staff should make every effort to complete the full panel of assessments scheduled for the EOT visit (Day 28). The reason for subject withdrawal must be documented in the electronic case report form (eCRF).

Withdrawn subjects will not be replaced.

[figure not shown]

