All subjects will also have an assessment using the NIAID ordinal scale score (see Appendix C) daily on Days 1 to 28/EOT. The NIAID score will be evaluated directly for inpatient subjects and assessed via a subject diary for outpatient subjects through Day 28.

After treatment is completed, subjects will undergo a follow-up visit on Day 35 (± 3 days) and a telephone follow-up on Day 60 (± 3 days). The purpose of the telephone follow-up is to assess survival status and evaluate for COVID-19 relapse. A telephone follow-up visit may be performed in lieu of the Day 35 follow-up visit if the subject is unable to attend in person.

DATA AND SAFETY MONITORING BOARD:

An independent Data and Safety Monitoring Board (DSMB) with multidisciplinary representation will be established to evaluate accumulating clinical trial data and to assess the ongoing safety of the clinical trial for the subjects enrolled. Interim safety assessments will be scheduled after the first group of 10 subjects has been enrolled and subsequently, as needed, to provide safety oversight for subjects in the clinical trial. Additional details will be provided in the DSMB charter.

STOPPING CRITERIA:

An independent DSMB will evaluate the safety and tolerability of the first 10 subjects after dosing and determine if it is acceptable to continue the clinical trial. However, safety and tolerability data will be reviewed on an ongoing basis by the Medical Monitor and stopping rules will be applicable starting with dosing of the first subject.

Subjects will be discontinued from dosing, but will continue to be followed in the clinical trial, if

[REDACTED]

DOSAGE FORMS AND ROUTE OF ADMINISTRATION:

ADX-629 and the corresponding placebo will each be administered orally as a tablet, at the discretion of the Investigator, without food, defined as no food for at least 2 hours prior to dosing and at least 1 hour after dosing. Each subject will receive either ADX-629 300 mg BID or placebo BID for up to 28 days. If a subject is temporarily unable to tolerate dosing, a temporary dose interruption of up to 2 days may be permitted, after discussion with the Medical Monitor. No dose reductions will be permitted.

ADX-629 and the corresponding placebo will each be available as a tablet for oral administration. Additional details can be found in the Pharmacy Manual.

ENDPOINTS:

The primary endpoint is the safety of ADX-629, determined by evaluation of the following:

- AEs;

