6.6 Early Termination Visit and Withdrawal Procedures

The EOT for subjects completing the clinical trial is Day 28. For subjects who are withdrawn from the clinical trial prior to completion, all Day 28 procedures (see Section 6.3.10) will be performed at an early termination visit. Subjects who are withdrawn and complete an early termination visit will also undergo a telephone follow-up at Day 60.

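### Protocol 4.3 permits ending trial participation, not only dosing, for reasons that can be related to outcome, and does not say how this fits its own rule that subjects off study drug stay in follow-up

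*Protocol*

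**What the plan says.** Protocol 4.3 opens its list with: "Participation of a subject in this clinical trial may be discontinued for any of the following reasons". The list concerns the trial, not the study drug. Three of its grounds matter here:

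- an SAE, clinically significant AE, severe laboratory abnormality or similar condition, but only one "which indicates to the Investigator that continued participation is not in the best interest of the subject";
- "Requirement of prohibited concomitant medication";
- "Subject failure to comply with protocol requirements or clinical trial-related procedures".

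The paragraph after the list takes another course. Unless consent for further follow-up is withdrawn, those who stop study drug "will continue with the clinical trial for acquisition of safety and efficacy assessments through the Day 60 telephone follow-up visit". The Stopping Criteria in the synopsis point the same way: "Subjects will be discontinued from dosing, but will continue to be followed in the clinical trial" (the triggers are redacted). Section 3.1 does likewise for a subject who is ventilated or cannot swallow a tablet: dosing stops, and monitoring for efficacy and safety goes on.

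Section 6.6 deals with those who leave: they have the Day 28 procedures at an early termination visit, followed by a Day 60 call. It lists no NIAID scoring after that visit and does not mention Day 35. Section 6.4 gives the Day 35 visit to all subjects. Section 8.4 directs withdrawal from the trial for pregnancy.

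**The concern.** Stopping a drug and leaving a trial are different events, and 4.3 does not keep them apart. A subject removed under the list during treatment has also stopped study drug, so both paragraphs of 4.3 reach the same person. With approximately 3 sites, one could keep such a subject in daily scoring and another could close the record after an early termination visit, each with support in the text.

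What is at stake is the NIAID score over Days 1 to 28, and with it time to recovery and the Day 1 to 28 proportions. An SAE, a laboratory abnormality or the need for a prohibited medicine can be related to how the subject is doing. If scoring stops for such a reason, the missing scores may differ systematically from the observed ones, and may do so unequally between arms. Section 8.2 adds weight: non-fatal COVID-19 progression unrelated to study drug is to be captured through the endpoints and not as an SAE. If scoring stops, the main record of later progression stops with it.

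**Working it through.** The plan states no withdrawal rate, power or effect size, so there is no figure to reproduce. The check has two parts.

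**The texts side by side.** Take a subject who stops study drug on Day 7 for a listed reason and has not withdrawn consent.

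- If the follow-up paragraph of 4.3 governs: safety and efficacy assessments continue through Day 60, which includes daily NIAID to Day 28 and the Day 35 visit.
- If the list and 6.6 govern: Day 28 procedures at an early termination visit, which under 6.3.10 include a NIAID score, then a Day 60 call. Under 6.5 that call records concomitant medications and AEs, and its purpose is survival and relapse. It cannot recover daily scores.
- Day 35 is unsettled: 6.6 does not mention it, and 6.4 applies it to everyone.

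Nothing in 4.3, 6.6 or the synopsis says which course applies.

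**What the SAP does with the gap.** SAP 3.1.2 uses nominal visits and does not say how an early termination score enters the Day 28 summary in 3.4.1. The readable SAP has no rule for missing NIAID scores. SAP 3.4.2 censors time to recovery at Day 28, with no rule for earlier withdrawal. SAP 3.2.2 requires study completion for the PP Population. Protocol 4.3 says withdrawn subjects are not replaced.

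**Size, as illustration.**

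Inputs from the documents: about 30 subjects randomized 2:1, so 30 × 2/3 = 20 and 30 × 1/3 = 10; NIAID daily on Days 1 to 28; scale 1 to 8. Assumptions: the day of withdrawal, and a withdrawal rate of 5% to 20%.

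- Daily scores lost after withdrawal on Day d = 28 − d. Day 7: 21 of 28 (75%). Day 14: 14 (50%). Day 21: 7 (25%).
- Planned scores = 30 × 28 = 840. Low case: 5% withdrawn (1.5 subjects) at Day 14 gives 1.5 × 14 = 21 scores, or 2.5%. High case: 20% withdrawn (6 subjects) at Day 7 gives 6 × 21 = 126, or 15%.
- One subject with unknown Day 28 status is 1/20 = 5% or 1/10 = 10% of an arm. The score could lie anywhere from 1 to 8, a span of 7, so the arm mean is uncertain by up to 7/20 = 0.35 or 7/10 = 0.70 points.

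**The case against.** The strongest reply is that the two paragraphs can be read together. The list is permissive. Its SAE, AE and laboratory ground needs the Investigator's judgement, so an SAE alone triggers nothing. The follow-up paragraph may be meant as the default that limits the list, or the two may cover different groups: off drug, and out of the trial. That stands against any claim that 4.3 automatically ends participation or flatly contradicts itself. It does not remove the overlap, because no text says which reading applies.

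A reader might also infer that data are lost for the sickest subjects. The documents do not support that. Subjects who are ventilated, cannot swallow a tablet or meet the dosing stopping criteria stay in follow-up. The note to exclusion criterion 14 permits dexamethasone after randomization on progression, so that use is not a prohibited medicine. Section 8.2 keeps most non-fatal progression out of SAE reporting. Non-compliance need not follow from worsening, and the excluded-medication text in 5.6.1 cannot be read, so the link for prohibited medication cannot be checked.

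Nor are later AEs simply lost. Section 8.1 collects AEs through the telephone follow-up, and the Day 60 call asks for them. A missing Day 35 visit is only an inference from the silence of 6.6.

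Finally, one could construct a case in which 2 of 10 placebo and 2 of 20 ADX-629 subjects do badly and are withdrawn, so that 8/10 against 18/20 (80% against 90%) becomes 8/8 against 18/18 (100% against 100%). The arithmetic is right, but it assumes the withdrawals, their outcomes and an available-case analysis that the SAP does not state. The SAP analyses efficacy in the ITT Population and divides deaths by all randomized, and the early termination visit itself yields a NIAID score.

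**Conclusion.** The point holds as an unresolved overlap. Section 4.3 permits participation to end for reasons that can be related to outcome, its next paragraph keeps subjects off drug in follow-up, and 6.6 lists no daily NIAID scoring once a subject is classed as withdrawn. Informative loss is therefore possible, not certain.

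Per subject the loss can be large: three quarters of the daily scores after a Day 7 withdrawal, in arms where each subject carries 5% or 10% of the weight. How many subjects would be affected is unknown; the overall range of 2.5% to 15% of planned scores rests on the assumed rate and timing. The key NIAID summary in SAP 3.4.1 is a descriptive change to Day 28. Daily scores still matter, because protocol 9.2.1 plans repeated-measures models over 28 days and time to recovery is defined by day. The trial is exploratory and not formally powered, so this is a recommended correction and not a fault that undermines the design.

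**What to change.** Reconcile the synopsis Stopping Criteria with protocol 3.1, 4.3, 6.4, 6.6 and 8.4 by defining two things separately: reasons for discontinuing study drug, and reasons for ending follow-up. State that subjects who stop study drug and have not withdrawn consent for follow-up continue NIAID scoring to Day 28 and the Day 35 and Day 60 contacts, as the follow-up paragraph of 4.3 already intends. Say in 6.6 whom the early termination visit is for and whether Day 35 applies to them.

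The clinical criteria for stopping dosing and the Investigator's judgement should stay unchanged. How the pregnancy rule in 8.4 fits is for the sponsor to decide.

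The cost is a wording amendment, plus a few more assessments for subjects off drug.

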5 CLINICAL TRIAL TREATMENTS

5.1 Treatment Groups

All subjects will receive either ADX-629 300 mg BID or placebo BID for up to 28 days. The study drug will be administered orally as a tablet, at the discretion of the Investigator.

5.2 Rationale for Dosing

The starting dose for ADX-629 is based on the nonclinical studies conducted to-date and the doses used in the Phase 1 healthy volunteer clinical trial. Subjects in this clinical trial received escalating single and multiple doses, and the highest strength tested was 600 mg BID for a period of 10 days.

